6.1. Primary Outcome Measures

The primary objective is to determine the safety and efficacy of YoBee in improving dry scalp conditions. Efficacy will be determined using the Investigator's Global Assessment (IGA) scale (Table 1), a 5-point assessment ranging from clear (0) to severe disease (4) and the Total Severity Scale (TSS) (Table 2), an assessment that averages erythema, scaling, and pruritus severity scores of scalp lesions. The TSS uses a 4-point scale ranging from none (0) to severe (3). Lastly, photographs of the scalp will be collected before and after treatment. Safety will be determined by contacting the patient via over the phone or through email to document adverse events and Overall Safety Score. The Overall Safety Score (Table 4) and the reporting of adverse events throughout the study will measure the safety of YoBee. The Overall Safety Score is a 4-point assessment ranging from “no signs of irritation” (0) to “patient discontinued due to irritation” (3). Participants will include the Overall Safety Score assessment in their daily journal.

An exploratory aim of this study is to find whether YoBee changes the microbiome after use for a dry scalp condition to more closely resemble healthy scalps. This will be accomplished by obtaining swab samples from the participants' scalps, before and after the treatment period. The samples will be analyzed using 16s RNA sequencing and internal transcribed spacer (ITS) sequencing. Additionally, the change in colony count of bacterial and fungal colonies on the scalp before and after the treatment will be assessed using the Replicate Organism Detection and Counting (RODAC) method. Finally, ScalpDex, a validated instrument, will assess the change in quality of life of participants. ScalpDex is a 23 question survey that will be administered electronically via RedCap to participants.

7. DATA DISCLOSURE AND SUBJECT CONFIDENTIALITY:

Subject medical information obtained as a result of this study is considered confidential, and disclosure to third parties other than the principal investigator and the co-investigators is prohibited. Data may only be disclosed in relation to compliance with mandatory state and federal disclosure laws, and will not be disclosed in any other circumstance. All reports and communications relating to subjects in this study will identify each subject only by their initials and study identification number. Medical information resulting from the subject's participation in this study may be given to the subject's personal physician or the appropriate medical personnel responsible for the subject's welfare. Data gathered as a result of this study are available to inspection on request by the Lurie Children's Hospital Institutional Review Board (LCHIRB).

8. EFFICACY ASSESSMENT

The efficacy of our trial will be measured by an 11-point scalp flaking scale (IGA). Second, we will employ 16S rRNA gene sequencing to analyze the composition of the scalp microbiome before and after treatment. Finally, efficacy toward reducing Staph colonization will be quantified via colony count of *S. aureus* scalp

cultures from patients plated on RODAC plates, and compared against each patient's baseline measurements.

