We aim to characterize the safety and efficacy of a topical preparation of *Lactobacillus sp.*, honey, and turmeric in an emollient base in restoring the scalps of those with dry scalp to more closely resemble the healthy scalps.

2. STUDY DESIGN AND SYNOPSIS:

This pilot study consists of participants diagnosed with dry scalp. Participants will receive the required topical vehicle with the treatment condition (containing dead bacteria) on their scalp. This study will consist of 15-40 participants' ages 1 years old to 17 years old and 20-40 participants 18 and older with a clinical diagnosis of dry scalp. Participants will be recruited either while visiting a dermatologist for a standard office visit, while visiting a pediatrician for a standard office visit, or by coming into Children's Healthcare Associates, Medical Dermatology, or our Northwestern research office to be assessed by a physician. Each study visit will take approximately 15-20 minutes.

No randomization will occur, as all participants will receive the active treatment. Each adult participant will apply the active treatment once daily for a study period of 14 days and discontinue using all other scalp management therapies. Each child participant (with the help of a caregiver, if needed) will apply the active treatment once every 2 to 3 days for a study period of 14 days and discontinue using all other scalp management therapies.

The primary goal of this study is to determine the safety and effectiveness of *Lactobacillus sp.*, honey, and turmeric in reducing dry scalp symptomology.

There are three goals in the comparison of these conditions:

- The first is to find the effectiveness of the active treatment in improving clinical disease severity. To accomplish this, an investigator will assess the severity of dry scalp before and after the treatment period using the 11-point flaking scale (Neumann 1996), respectively.
- The second goal is to determine whether the active treatment is safe. This will be accomplished by contacting the patient via over the phone and through daily emails designed to document adverse events and Overall Safety Score. The Overall Safety Score is a 4-point assessment ranging from "no signs of irritation" (0) to "patient discontinued due to irritation" (3). Participants will be asked about the Overall Safety score at the halfway point and the end point of the study.
- The third exploratory goal is to determine whether the microbiome can be changed. This will be

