accomplished by obtaining swab samples from the participants' scalps, before and after the treatment period. The samples will be analyzed using 16s RNA sequencing and internal transcribed spacer (ITS) sequencing. Additionally, the change in colony count of bacterial and fungal colonies on the scalp before and after the treatment will be assessed using the Replicate Organism Detection and Counting (RODAC) method. We aim to characterize the effects of *Lactobacillus* sp., honey, and turmeric on dry scalps.

- Finally, this study will determine the quality of life of participants before and after the treatment period. Quality of life will be calculated using the ScalpDex tool, a validated 23-item instrument that explains the way that patients with scalp dermatitis are affected by symptoms, functioning, and emotions.

3. STUDY OBJECTIVES:

The first goal of this study is to determine the effectiveness of introducing *Lactobacillus* sp., honey, and turmeric, in reducing dry scalp symptomology.

Hypothesis 1a: Participants' scalps treated with vehicle plus *Lactobacillus* sp., honey, and turmeric preparation will exhibit decreased dry scalp severity on assessment by an investigator when compared to the scalps before treatment, as measured by an 11-point flaking scale.

The next objective is to determine the safety of introducing *Lactobacillus* sp., honey, and turmeric, in reducing dry scalp symptomology

Hypothesis 2a: The product containing *Lactobacillus* sp., honey, and turmeric will be safe for participant's scalps as measured by the Overall Safety Score and patient logs.

The final objective of this study is to compare the determine if an active *Lactobacillus*, honey, and turmeric topical preparation changes the microbiome after use for a dry scalp condition to more closely resemble healthy scalp

Hypothesis 3a: Participants' scalps treated with the active *Lactobacillus*, honey, and turmeric preparation will have a microbiome similar to those with healthy scalps.

4. STUDY POPULATION:

We aim to recruit participants with diagnosed dry scalp and with clinical signs on the scalp. Recruitment will consist of male and female participants. This will include 15-40 children between the ages of 1 year to 17 years old, and 20-40 adults over the age of 18.

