4.1.2. Exclusion criteria

- e. Infants younger than 1 year old
- f. Patients diagnosed with other scalp diseases such as psoriasis, tinea capitis, and pediculosis capitis
- g. Systemic steroid or oral antibiotic use during the past two months
- h. Allergy to any of the preparation components

5. STUDY PROCEDURES:

For this study, 20-40 subjects over the age of 18 and 15-40 subjects aged 1 year to 17 years, all with a clinical diagnosis of dry scalp, will be enrolled. 5-10 adults participants will be enrolled and complete the study prior to enrolling children. All participants who fit the inclusion criteria and are currently being seen at either a Lurie Children's location, Children's Health Associates, the Medical Dermatology Associates of Chicago, or other outside locations, will be verbally invited to participate in the study, immediately following their regularly scheduled appointment, by a study coordinator will be administered informed consent. Additionally, those not able to attend a standard office visit, will come into our Northwestern office to be assessed by a board-certified physician. Study staff will identify potentially eligible study patients from clinic databases or those who have previously shown interest and mail or email these patients a letter with information on the study protocol, eligibility criteria and participant compensation, as well as instructions to contact study staff if interested in participation. We will also wait a week after mailing the potentially eligible study patients and call and/or e-mail them to see if they are interested in participation.

A research coordinator will obtain bilateral culture swabs of the scalp, in order to assess the composition of the local bacterial community. A research coordinator will also obtain bilateral cultures of each participant's scalp via the RODAC plate method in order to assess the burden of *S. aureus* on the skin. Swab and culture samples will be sent to the lab of [name] at Lurie Children's or to [name] lab at Rush University to be processed via 16s rRNA sequencing and colony count, respectively. Lastly, a board-certified physician will assess the clinical severity of the participant's dry scalp via the 11-point flaking scale. Photographs will be taken as record for both adult and child studies.

Each participant will then fill out a baseline survey including demographics in REDCap.

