10.1 Power analysis

The study is powered. An important goal of this study is to determine the changes in severity score pre/post treatment based on a 5 point severity scale. As we expect a decrease in severity score based off IgA scale post-treatment, we powered the study based on the ability to detect at least a one point difference in change of severity score with 80% power and an alpha level of 0.05.

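### The primary efficacy scale is contradictory: an 11-point flaking scale in five places, a 5-point IGA plus TSS under Primary Outcome Measures, and a power statement on a 5-point scale

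*Combined protocol and SAP*

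**What the plan says.** Five places in the combined protocol and SAP make an 11-point flaking scale the efficacy measure:

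- Section 2 (synopsis): the investigator rates the "severity of dry scalp before and after the treatment period using the 11-point flaking scale".
- Section 3, Hypothesis 1a: severity is to fall "as measured by an 11-point flaking scale".
- Section 5, baseline: a physician rates "dry scalp via the 11-point flaking scale".
- Section 8: "The efficacy of our trial will be measured by an 11-point scalp flaking scale (IGA").
- Section 10: the flaking survey is described as an 11-point measure.

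Two places use something else:

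- Section 6.1, the only section headed Primary Outcome Measures, determines efficacy by the IGA, "a 5-point assessment ranging from clear (0) to severe disease (4) and the Total Severity Scale (TSS"). The TSS averages erythema, scaling and pruritus scores and runs from 0 to 3. The flaking scale is not mentioned.
- Section 10.1 says that the study is powered, and describes the goal as "changes in severity score pre/post treatment based on a 5 point severity scale". It continues "As we expect a decrease in severity score based off IgA scale post-treatment", and the claim is "the ability to detect at least a one point difference in change of severity score with 80% power" at an alpha of 0.05.

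**The concern.** There are two competing main instruments, and one name is used for both. IGA is a 5-point scale in Section 6.1 and in Section 10.1 (where it is spelled IgA). It is the flaking survey in the adult day-14 sentence of Section 5 and the 11-point scale in Section 8. A third scale, the TSS, is listed under Primary Outcome Measures, but no procedure in Sections 5 and 6 names it.

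Every participant receives active treatment and there is no control, so the before/after change in severity is the whole primary efficacy result. With three candidate scales and no rule for choosing among them, an analyst could report whichever improved most, and the protocol would support any of the three. The power statement is also detached from Hypothesis 1a: it is framed on a 5-point scale, while the hypothesis is framed on an 11-point one.

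**Working it through.** **1. Can the passages be reconciled?**

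| Place | Scale |
|---|---|
| Section 2, synopsis | 11-point flaking |
| Section 3, Hypothesis 1a | 11-point flaking |
| Section 5, baseline | 11-point flaking |
| Section 5, day 14, adults | flaking survey, labelled IGA |
| Section 5, day 14, children | IGA |
| Section 5, Study Schema, both visits | flaking survey |
| Section 6, baseline and day 14 (adults and children) | flaking survey |
| Section 6.1, Primary Outcome Measures | 5-point IGA (0–4) plus TSS (0–3) |
| Section 8 | 11-point flaking, labelled IGA |
| Section 10 | 11-point flaking |
| Section 10.1 | 5-point, labelled IgA |

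- *Complementary endpoints?* No. One name cannot mean both a 5-point and an 11-point instrument, and Section 6.1 leaves out the scale on which Hypothesis 1a depends.
- *Lost tables?* No. The prose itself gives the ranges and the number of points.
- *Settled by the analysis section?* No. Section 10 gives units of measurement. It names no primary variable, hierarchy or test.
- *Settled by the procedures?* Only partly. They mostly collect the flaking survey. The recording ambiguity is confined to the IGA label, chiefly the child day-14 sentence in Section 5 against the child day-14 sentence in Section 6.

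**2. Cost of an open choice.** Suppose three scales are each tested at 0.05 and any success counts. If the tests are independent, the false-positive chance is 1 − 0.95³ = 0.143. If they are fully correlated it is 0.05. For an assumed pairwise correlation of 0.5 to 0.9 it is about 12.5% down to 8%.

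**3. The stated 80% power.** It cannot be reproduced: Section 10.1 gives the difference (1 point), alpha (0.05) and power, but no SD of change, test, sidedness or N. The planned enrolment is 20–40 adults and 15–40 children, 35–80 in all.

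**4. Illustration of why the scale matters.** Assumptions, none from the documents: paired t-test; SD of change 25% of the scale range; the 11-point scale coded 0–10. The one-point target is carried over, although the plan sets it only for the 5-point scale. Power is taken from a noncentral t with n − 1 degrees of freedom and noncentrality (δ/SD)·√n.

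- 5-point scale: SD = 0.25 × 4 = 1.0. At n = 20, noncentrality = 1 × √20 = 4.47.
- 11-point scale: SD = 0.25 × 10 = 2.5. At n = 20, noncentrality = 0.4 × √20 = 1.79.

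| One-point change | Power, two-sided | Power, one-sided |
|---|---|---|
| SD 1.0, n = 20 | 98.9% | 99.6% |
| SD 2.5, n = 20 | 39.7% | 53.2% |
| SD 2.5, n = 40 | 69.4% | 80.0% |
| SD 2.5, n = 35 (pooled minimum) | 63.3% | 75.0% |
| SD 2.5, n = 80 (pooled maximum) | 94.2% | 97.1% |
| SD 1.5, n = 20 | 80.7% | 89.0% |
| SD 3.0, n = 20 | 29.4% | 41.8% |

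The n needed for 80% power (two-sided / one-sided) is 10 / 8 at SD 1.0, 20 / 16 at SD 1.5, 52 / 41 at SD 2.5 and 73 / 58 at SD 3.0. At n = 20, a one-point change has 80% power only if the SD is at most 1.51 two-sided or 1.73 one-sided.

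One point is 1/4 = 25% of a 0–4 range but 1/10 = 10% of a 0–10 range. If the target were scaled as well (2.5 points at SD 2.5), δ/SD = 1.0 and power at n = 20 returns to 98.9% two-sided. Power on the 11-point scale can therefore fall on either side of 80%.

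**The case against.** The strongest reply is that the plan does contain a working primary scale. Hypothesis 1a names only the flaking scale, Section 8 lists it ahead of sequencing and colony counts, and the visit procedures mostly collect it. This narrows the problem but does not remove it: the section headed Primary Outcome Measures omits that scale, and the power statement sides with Section 6.1.

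The 14.3% is an upper bound. No passage says that any success counts, and independence is implausible for ratings of the same scalp. Section 6.1 joins IGA and TSS, which could mean that both must improve, and that would not inflate the error. This stands, so the figure should be read as the cost of leaving the choice open, not as the plan's error rate.

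The power illustration rests on an assumed SD, coding and test and on a transferred target, and it shows no underpowering. That is also correct. The missing power inputs would be a defect even with one consistent scale.

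The TSS point is limited to what Sections 5 and 6 describe. The content of the follow-up questionnaire is not given, so some part of the TSS might be collected there.

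Finally, this is a single-arm pilot with no stated decision rule. However, it states an efficacy hypothesis and says that it is powered, so it needs a defined primary result.

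**Conclusion.** The concern holds, with high confidence, and must be fixed. It rests on the current text alone: five places state 11 points, Section 6.1 states a 5-point IGA plus TSS, Section 10.1 powers on 5 points, and IGA names both instruments. No passage resolves this, so the primary efficacy result is undefined. That is the main harm. The numerical consequences are conditional on the assumptions stated above and are secondary. The 80% power is uncheckable and is not linked to the scale in Hypothesis 1a, but it has not been shown to be wrong.

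**What to change.** Before outcome data are reviewed:

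1. Name one primary efficacy variable: change from baseline to day 14 on one scale, chosen as the instrument actually intended and scored.
2. Use IGA for one instrument only.
3. Make the TSS and any other retained scale secondary, with a collection point at both visits, or delete it.
4. Restate Section 10.1 on the chosen scale with the target difference, the assumed SD of change and its source, the test and its sidedness, and the N (per cohort or pooled). Report whatever power results.

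**Cost.** Keeping the 11-point scale needs the fewest edits: Sections 6.1 and 10.1, plus three IGA labels (both day-14 sentences in Section 5, and Section 8). Choosing the 5-point IGA means changing Sections 2, 3, 5, 6, 8 and 10, including the visit procedures. Each retained secondary scale adds an assessment at both visits, and scales not chosen lose primary status.

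Section 10.1 needs a new justification, not just new wording. The stated power may fall below 80%, or the detectable difference may have to be larger. On the 11-point scale, the illustrative requirement for one point is 52 (two-sided) or 41 (one-sided) at SD 2.5, and 20 or 16 at SD 1.5. A pooled N of 35–80 could cover these, depending on enrolment.

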Recent studies have highlighted the potential role of changes in the skin bacterial and fungal community—the skin microbiome—in exacerbating inflammation of atopic skin. The changes show differing dominating bacterial and fungal strains in healthy and diseased skin (Park 2017). Lesional skin has been shown to be dominated by *Staphylococcus* bacteria and contain a lower microbial diversity than adjacent non-lesional skin (Kong 2012, Seite 2014). It is hypothesized that *Staphylococcus aureus* plays a critical role in the pathogenesis of eczema: the density of *S. aureus* in eczema patients can be staggering at 10^7 colonies per square centimeter of atopic skin, representing a far greater burden than those observed in other forms of skin inflammation (Lin 2007, Cho 2001). *Staphylococcus* is also a major bacteria found on atopic scalps (Park 2017). Though the precise link between dysbiosis, eczema, and dry scalp in humans remains unclear, these results warrant further investigation into the role of antimicrobial therapy in reversing dysbiosis and its' potential exacerbation of disease severity.

The use of hydrating emollients is effective on atopic skin, in which dry cracks allow irritants to pass and exacerbate the condition (Hanifin et al 2004). Emollients have been found to change skin communities from a disease to healthy state (Seite 2014). Of especial relevance, a 2014 study showed that topically allied emollients containing *Lactobacillus sakei* were effective in a split body trial at reducing common symptoms of eczema (Park 2014). As topical therapy, honey has been shown to work synergistically with antibiotics to treat methicillin-resistant *S. aureus* (Liban 2013). Honey possesses the antibacterial potency needed to stop the growth of *S. aureus*. and histologic studies show early decreases in inflammation, better infection control, and faster healing times (Lusby 2002). In addition, curcumin, the

active ingredient in turmeric, has also shown to be beneficial in skin disease. Although research on curcumin is not extensive, it has demonstrated antioxidant and anti-inflammatory properties in preclinical trials. Its lack of toxicity, even at high doses, makes it an attractive, natural treatment option (Thangapazham et al 2007).

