Participants will be supplied with the scalp treatment and relevant instructions. Participants will be instructed to apply the preparation to their scalp. Adults will apply the scalp treatment on the site of active dry scalp once per day at home at a consistent time, every day for 14 days. Children will apply the hair care regimen at home at a consistent time two to three times a week over a 14-day period. -. Participants will be instructed to discontinue their regular scalp-care therapies. Adult participants will be contacted daily via email or telephone regarding scalp care regimen, usage of treatment, and any adverse events. Child participants will be contacted weekly via email or text regarding scalp care regimen, usage of treatment, and any adverse events. One week from the baseline visit (7 days), the participant will be contacted via phone, text or email to complete surveys regarding treatment experience and to confirm correct usage of treatment. Fourteen days following the baseline visit, adult participants will be seen, where repeat scalp cultures will be obtained via the swab and RODAC methods, and a repeat scalp flaking survey (IGA) (with photographs) will be assessed by a physician. Final experience surveys will be administered via REDCap. Fourteen days following the baseline visit, child participants will attend a secondary visit, where a physician will assess the participants' scalp and re-evaluate the IGA placement.

Study Schema

VISIT 1: (baseline)

- Recruitment and electronic informed consent of participants via REDCap.
- Obtain baseline scalp culture skin swabs from participant for microbiome diversity analysis.
- Obtain baseline scalp cultures from participant via RODAC method to obtain initial bacterial burden level. The RODAC (Replicate Organism Detection and Counting) method is used to measure the number of colony forming units (CFU) per skin surface area. The primary purpose of the RODAC method is to monitor presence and number of microorganisms as determined by the appearance of colonies on the surface of an agar medium.
- Local scalp flaking survey performed to the participant by investigator. Photographs will be taken.
- Administer baseline demographics survey via REDCap.
- Demonstrate/teach patients the treatment regimen. The treatment for adults will be applied daily for 14 days for 5 minutes. The treatment for children will be applied 2 to 3 times a week over the course of 14 days for 5 minutes.

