- Instruct adult participants to respond to the daily scalp care emails or phone calls. Instruct child participants to weekly scalp care emails, text messages, or phone calls.- Provide participants with all study materials, including instruction handout.
- Instructions for adults will be given stating: Wash your hands and make sure scalp/hair is dry, and then apply the treatment to your entire scalp. Massage the treatment in, wait around seven minutes, and then rinse it from your scalp. Please be sure to apply the treatment daily. Instructions for children will be given stating: Wash your hands and make sure scalp/hair is dry, and then apply the treatment to your entire scalp. Massage the treatment in, wait approximately five minutes, and then rinse it from your scalp. Please be sure to apply the treatment 2 to 3 times a week.

FOLLOW-UP:

- Study coordinator will contact participant or caregiver via phone or email daily to ensure safety of treatment regimen. [name] will follow-up with patients if adverse events are reported.
- Quality of life and overall safety score surveys will be sent to participants at the 7 day mark.

VISIT 2 at Lurie Children's, Northwestern University, or Medical Dermatology Associates of Chicago: (14 days after baseline)

- Obtain scalp culture skin swabs from patient for microbiome diversity analysis.
- Obtain scalp cultures from patient via RODAC method to obtain final bacterial burden level.

- Local scalp flaking survey performed to patient by investigator. Additional photographs will be taken.
- Ask participants to fill out the follow-up questionnaire via REDCap during the visit on a study iPad.

Events performed outside of patient visits:

-Skin swabs and RODAC plates will be transported from the collection site to the laboratory of [name] or to [name] lab at Rush University. The team will use an insulated carrier to transport the samples directly following each visit.

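### The day-14 S. aureus plate count follows use of a honey product and the baseline count does not, so a fall cannot be attributed to reduced colonization alone

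*Combined protocol and SAP*

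**What the plan says.** Section 8 (Efficacy Assessment) names the S. aureus colony count as the measure of efficacy against Staph colonization: "cultures from patients plated on RODAC plates, and compared against each patient's baseline measurements". Section 6.1 places the RODAC counts under an exploratory aim.

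The Study Schema in section 5 describes RODAC as a count of colony-forming units per skin surface area, "as determined by the appearance of colonies on the surface of an agar medium". Visit 1 has the step "Obtain baseline scalp cultures from participant via RODAC method to obtain initial bacterial burden level". Visit 2, 14 days later, has "Obtain scalp cultures from patient via RODAC method to obtain final bacterial burden level".

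Between the two, adults use the product "once per day at home at a consistent time, every day for 14 days". The instructions in section 5 tell participants to "apply the treatment to your entire scalp", wait and then rinse. The adult wait is about seven minutes in the instructions but five minutes in the Study Schema; these two places must be reconciled. Children apply the product two to three times a week.

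The background section gives the rationale for honey: "Honey possesses the antibacterial potency needed to stop the growth of *S. aureus".

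Section 2 states that nobody is randomized and everyone receives the active treatment. Section 10 plans total bacterial DNA by quantitative PCR and 16S relative abundance. It names no statistical test for the colony counts.

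**The concern.** A colony count registers only organisms that grow on the agar. If product residue reaches the agar with the sample, it can hold back growth there, and the plate will show fewer colonies than the scalp would otherwise yield. Study product can have this effect at day 14 but not at baseline.

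A parallel group using a comparable product without the inhibitor, or plates that neutralise it, would help to separate the two explanations. The plan has neither. Section 8 would therefore read a lower day-14 count as fewer staphylococci on the scalp when part of the fall might arise on the plate. At stake is the Staph-reduction statement, not the flaking or severity result.

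**Working it through.** **Step 1. Compare the two plates.**

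| | Baseline plate | Day-14 plate |
|---|---|---|
| Study product used beforehand | None | Daily in adults, over the whole scalp |
| Interval since last study application | Not applicable | Not stated; about 0 to 1 day for adults if the daily schedule is followed |
| Neutralising agar or recovery check | Not mentioned | Not mentioned |
| Control arm with the same exposure | None | None |
| Previous scalp products | Possible: stopped at enrolment, and section 4.1.2 sets no topical washout | Should have been stopped for 14 days |

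For children, the schema lists RODAC at Visit 2 without distinguishing age groups, but the child-specific day-14 text in sections 5 and 6 lists only the physician's assessment and, in section 6, a questionnaire. The comparison is therefore certain only for adults.

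**Step 2. Is there a planned figure to reproduce?** No. The power statement in section 10.1 concerns the severity score. The documents give no SD, test or effect size for colony counts.

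**Step 3. Illustrate the possible size.** From the documents: 20 to 40 adults. Assumed: no true change on the scalp; a two-sided 0.05 paired t test on log10 CFU; SD of change 0.5 to 0.8 log10; a fraction f of colonies suppressed on the day-14 plate only.

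Apparent fall: δ = −log10(1 − f). Noncentrality: λ = (δ / SD) × √n. Probability of a false significant fall: P(T > t(0.975, n − 1)), with T noncentral t on n − 1 degrees of freedom and noncentrality λ.

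Example, f = 0.25, n = 20, SD = 0.5: δ = −log10(0.75) = 0.125; λ = (0.125 / 0.5) × √20 = 1.117 (unrounded δ); critical value 2.093; probability 0.185.

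| f | δ (log10) | n = 20, SD 0.8 | n = 20, SD 0.5 | n = 40, SD 0.8 | n = 40, SD 0.5 |
|---|---|---|---|---|---|
| 10% | 0.046 | 0.043 | 0.058 | 0.054 | 0.081 |
| 25% | 0.125 | 0.097 | 0.185 | 0.160 | 0.338 |
| 50% | 0.301 | 0.359 | 0.724 | 0.641 | 0.960 |

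With no artefact, the rate in this direction would be 0.025. Suppression of about half could produce a convincing false fall; suppression of a tenth would matter little. The documents do not show which applies.

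**The case against.** The case against is substantial, and most of it limits the point rather than removing it.

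- **Residue is not shown.** The product is rinsed off after some five to seven minutes. The documents give no honey concentration, no residual amount and no agar type, and the background statement concerns honey as a topical therapy, not traces after rinsing. An effect near zero is possible. This stands.
- **Transfer to the agar is an inference.** The documents report counts per skin surface area from RODAC plates but do not describe how the plate meets the scalp. Direct contact fits that description but is assumed here.
- **The direction is not certain.** A reader might infer that the bias must favour the product. The documents do not support that: residue of an earlier scalp product could lower the baseline count by the same mechanism. The net direction is unknown.
- **Other measures do not depend on growth.** Quantitative PCR and 16S could expose a discrepancy. They do not replace the count, because PCR gives total bacterial DNA and 16S gives percentages, and the plan does not say that either will be used to check it.
- **The false-positive rates are constructed.** The plan contains no test for CFU, so these rates are not properties of the trial. They show only the size of suppression that would matter.
- **The count is exploratory in section 6.1.** This stands and limits the weight of the point, although section 8 still calls the result efficacy.

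What survives is that the plan does not allow the two explanations of a fall to be told apart.

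**Conclusion.** The point holds as a limit on interpretation. A fall in S. aureus RODAC count from baseline to day 14 would show fewer culturable organisms on the plate. Under the current plan it would not by itself show reduced colonization of the scalp.

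The size cannot be derived from the documents. Under the stated assumptions it runs from slight (4% to 8% false significant falls at 10% suppression) to serious (36% to 96% at 50%). The conclusion rests on some residue surviving the rinse and reaching the agar, which is plausible from the plan's own account of honey but not established.

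Two stronger readings go too far. The documents do not show that an observed fall would be an artefact. Nor do they suggest that the trial's main efficacy result is compromised: the physician's severity assessment does not depend on growth on agar. This is a cheap improvement to consider, not a defect that invalidates the trial.

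**What to change.** In sections 5 and 8:

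1. Specify one neutralising contact agar, the same at both visits, from the first participant.
2. Record the time from last application to the day-14 sample.
3. If plates have already been taken on non-neutralising agar, keep that agar. Switching partway would leave some participants with different media before and after treatment. Report the result as a change in culturable count with carry-over inhibition not excluded, and not as reduced Staph colonization.
4. In either case, read the count alongside the planned qPCR total DNA and the 16S Staphylococcus share. Total DNA multiplied by the share gives an approximate Staphylococcus quantity that does not depend on growth. It is not specific to S. aureus, so it supports the count rather than replacing it.

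The cost is a possible change of agar, one extra recorded time and a few sentences in the protocol. No patient procedure is added. The downside is a slightly weaker staph claim if step 3 applies.
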